4.3 Definition of end of study

The study will end when all patients have completed the treatment period and 150-day safety follow-up after the last dose of PDR001 or 30 days after the last dose of NIR178 whichever occurs later, and at least 80% of patients have completed at least 24 months of survival follow up from start of study therapy. Additionally, if another clinical study becomes available that can continue to provide study treatment in this patient population, all patients ongoing are transferred to that clinical study and all discontinued patients have completed the safety follow-up period. The follow-up for disease progression and survival will not be performed or pursued (see [Section 7.1.5.1](#)) At the end of the study, every effort will be made to continue provision of study treatment to patients who in the opinion of the investigator are still deriving clinical benefit through designated post-trial access programs or roll-over protocols, provided patient meets all eligibility criteria.

Refer to [Section 10](#) for details of timing of the primary analysis and final reporting of data.

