12-Apr-2023	Prior to final DB Lock	Major/Minor changes	
Final Amendment 2 (v2)
 
Major changes
 
 - Updated list of abbreviations - Tightened the study design with regards to Protocol Amendments, introduced terminology for treatment indications, clarified contradictory statements and removed duplicacy of information. - Distinguished efficacy and safety treatment groups for reporting on Part 1. Treatment indication precisely defined. - Precisely defined date of first/last administration of a study drug and study treatment - Corrected formula for Study day - Introduced different types of follow-ups as part of post-treatment period - Revised definition of Full analysis set - Revised definitions of IG analysis sets - Corrected the duration of exposure for Part 2 intermittent dosing - Aligned the organization of treatment indications with those mentioned Section 1.1.1 and Table 2-4 - Added a sentence to allow addition of any new qualifying treatment indication to inform the model. - Clarified that Secondary efficacy endpoints are to be evaluated in all Treatment groups contributing to primary efficacy objective. - Time to event endpoints to be estimated for trt groups >= 10 patients - Added precise definition of “sufficient” number of patients for change from baseline PSA analysis. - Clarified the criteria for summarizing efficacy endpoints for unknown RAS status. - Moved the paragraph on Safety summary from Section 2.1.1.5 to the right section under Section 2.6.2 - Tightened the reporting of AEs, SAEs, Deaths in line with the protocol with listings required on Screen failure patients. - Clarified that AESIs associated with combination trt will be reported using PDR001-specific eCRS . 	
 • List of abbreviations • Section 1.1 and sub-sections. • Section 2.1 • Section 2.1.1.2 • Section 2.1.1.3 • Section 2.1.1.5 • Section 2.2.1 • Section 2.2.4 • Section 2.4.1.1 • Section 2.5.2 • Table 2-4 • Section 2.5.2 • Section 2.6.1 • Section 2.6.1 • Section 2.6.1 • Section 2.6.1 • Section 2.6.2 • Section 2.6.2.1 • Section 2.6.2.2

Date	Time point	Reason for update	Outcome for update	Section and title impacted (Current)

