The following rules will be followed for reporting results unless stated otherwise:

- Part 1: In general, all TFLs will be presented by *treatment indications* unless specified otherwise.

- Disposition, demographics and baseline characteristics: Treatment groups at the most granular levels of treatment indication will be used for reporting on disposition, analysis sets, demographics, disease history, prior treatment and other baseline characteristics. If in the given programming environment, presentation of summaries on all the treatment groups is visually constraining, then these summaries may be presented separately for safety and efficacy using their respective consolidated treatment groupings as defined below.
- Safety/PK/IG: Treatment groups at the dose level of any treatment indication consolidating the categories of indication (consolidated by tumor types with no sub-grouping) will be used for reporting on safety and related endpoints like PK/IG.

█ [REDACTED]

- Part 2: All TFLs will be presented by the treatment dosing schedule.
- Part 3: If done, the presentation of TFLs will be similar to Part 1; however, if the indications selected from Part 1 do not have categories, then the Part 3 summaries may be consolidated with Part 2 for condensed CSR reporting.

Japanese safety run-in study

The data from this study is planned to be reported in the CSR separately from the Phase II study regardless of the Japanese patients' participation in the latter. However, for the brevity of CSR reporting, if deemed necessary, its reporting may be consolidated with safety reporting of Part 2. The efficacy data from this cohort will not be summarized but only listed.

Note: In a scenario that the results from part2, part 3 or the Japanese safety run-in are presented consolidatively and sorting on output data is involved for better interpretation of the results (e.g., AE summaries), then the results will be presented by study parts (part2, part 3, Japanese safety run-in) within the same output to have their own independent sorting.

Qualitative data (e.g., gender, race, etc.) will be summarized by means of contingency tables (frequencies and percentages) by treatment group; a missing category will be included as applicable. Percentages will be calculated using the number of patients in the relevant population or subgroup as the denominator.

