2.1.1.5 On-treatment assessment/event and observation periods

The overall observation period will be divided into three mutually exclusive segments:

pre-treatment period: from day of patient’s first informed consent to the day before first administration of study treatment

on-treatment period: from date of first administration of study treatment to 30 days after date of last actual administration of study treatment (including start and stop date). This period constitutes ***safety follow-up*** on all patients for 30 days after the last administration of study treatment.

post-treatment period: starting at day 31 after the last administration of study treatment. This period will constitute the following follow-up periods:

- ***extended safety follow-up period:*** all patients receiving PDR001 will continue to have safety evaluations for 150 days after the last dose of PDR001 or 30 days after the last dose of NIR178, whichever occurs later.
- ***disease progression follow-up period:*** Patients who discontinue study treatment for any reason other than death, disease progression per confirmed iRECIST or per Cheson (for DLBCL) or per PCWG3 guidance (for mCRPC) while on treatment, clinical deterioration or clinical progression, lost to follow-up, consent withdrawal or study termination, will have tumor evaluation assessments every 8 weeks (+/- 7 days) during the first 40 weeks,

and every 12 weeks (+/- 7 days) thereafter until disease progression, death, loss to follow-up or withdrawal of consent, whichever occurs first.

- **survival follow-up period:** Upon completion of the 150-day safety follow-up or disease progression follow-up, all patients (except for those in Japanese safety run in) will be followed for survival every 12 weeks until any of the following events (whichever occurs first): death, withdrawal of consent, loss to follow-up or at least 24 months from the first dose of study treatment.

Patients enrolled to another clinical study or alternate treatment (Protocol Section 4.3) will not have follow-up for safety, disease progression and survival assessments performed.

If dates are incomplete in a way that clear assignment to pre-, on-, post-treatment period cannot be made, then the respective data will be assigned to the on-treatment period.

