2.2.1 Full analysis set

For the Phase II - Part 1 and Part 3 and for the Japanese safety run-in study, the Full Analysis Set (FAS) comprises all patients who received at least one full or partial dose of assigned combination of study drugs. Patients will be analyzed according to the planned, which is the assigned treatment.

For Part 2 of the study, the FAS comprises all patients randomized to a study treatment, which in this case is treatment dosing schedule. According to the intent to treat (ITT) principle, patients will be analyzed according to the treatment they have been assigned to during the randomization procedure.

Unless otherwise specified, misrandomized patients (misrandomized in the interactive response technology (IRT) system) will be excluded from the full analysis set. Misrandomized patients include patients who are screen-failures, but have been randomized by the investigator before eligibility was finally assessed, however have not been treated. If patients were re-screened and successfully randomized, they will be included in the randomized set according to the dosing schedule treatment assigned in the last randomization.

The FAS will be used for all listings of raw data. Unless otherwise specified, the FAS will be the default analysis set used for all analyses.

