2.6 Analysis supporting secondary objectives

2.6.1 Efficacy objectives

The secondary objective is to assess the efficacy of NIR178 in combination of PDR001 using ORR per iRECIST, and other efficacy measures including disease control rate (DCR), duration of response (DOR), progression free survival (PFS) and 2 year overall survival (OS) by both RECIST v1.1 and iRECIST for solid tumors, by PCWG3 guidance (see Protocol Appendix 5) for mCRPC, and by [Cheson et al \(2014\)](#) for DLBCL.

These efficacy endpoints will be summarized for all the treatment groups contributing to the analysis of primary efficacy objective (see [Section 2.1](#) general analysis conventions).

ORR:

Overall response rate (ORR) is defined as the proportion of patients with best overall response (BOR) of immuno-related complete response (iCR) or immuno-related partial response (iPR), as per local review and according to iRECIST (see Protocol Appendix 3 for details) for solid tumors.

ORR as per iRECIST will be provided for each treatment indication along with corresponding 95% confidence interval (CI).

DCR:

DCR is the proportion of patients with a best overall response of CR, PR or stable disease (SD). DCR will be summarized by treatment indication with accompanying 95% confidence intervals.

OS, PFS and DOR:

OS is defined as the time from date of start of treatment to date of death due to any cause. If a patient is not known to have died, OS time will be censored at the date of last contact. The 2 year OS rate is the proportion of patients with at least 2 years of OS.

PFS is defined as the time from start of treatment date to date of the first documented disease progression or date of death, whichever happens first. If a patient has not had the event at the date of analysis cut-off, PFS will be censored at the time of the adequate tumor assessment before the cut-off.

For patients with a confirmed CR or confirmed PR, the DoR is the time from date of first documented response (CR or PR) to date of first documented progression or death due to underlying cancer, whichever happens first. If progression or death has not occurred at the date of analysis cut-off, then DoR will be censored at the date of last adequate tumor assessment before the cut-off.

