Kaplan-Meier (KM) plots and estimates for time-to-event endpoints including OS, PFS, and DOR will be presented for treatment groups of size ≥ 10 patients with estimable median. Median with accompanying 90% confidence intervals along with KM estimates for PFS and OS at 4, 6, 9, 12, 18 and 24 months will be reported.

For mCRPC patients, PSA at each time-point will be listed and **change from baseline in PSA** may be plotted and summarized if there are sufficient (≥ 10) patients.

All efficacy data from the patients from Japanese safety run-in part will be listed separately. These patients will not be summarized with the other patients.

All efficacy data from the non-HNSCC patients and melanoma IO naive patients will be listed separately and will not be summarized with the other patients. All efficacy data from patients with unknown RAS status will be summarized as a separate group with all other patients using estimable endpoints (enough patients for the endpoints to be estimated); otherwise, the efficacy data will be listed.

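### SAP 2.6.1 shows Kaplan-Meier output for OS and PFS only where the median can be estimated, so presentation depends on the result; the 2-year OS rate is also not tied to the 24-month Kaplan-Meier estimate

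*SAP*

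**What the plan says.** SAP 2.6.1 opens its list of secondary efficacy endpoints with a general commitment: "These efficacy endpoints will be summarized for all the treatment groups contributing to the analysis of primary efficacy objective". It then defines OS, with censoring at last contact, and adds: "The 2 year OS rate is the proportion of patients with at least 2 years of OS". The following paragraph on Kaplan-Meier output sets two conditions. Plots and estimates for OS, PFS and DoR "will be presented for treatment groups of size ≥ 10 patients with estimable median". The next sentence plans medians with 90% confidence intervals, and Kaplan-Meier estimates for PFS and OS at six times from 4 to 24 months.

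Three other places bear on the rule:

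- Protocol 10.5.1 plans Kaplan-Meier plots for DoR, PFS and OS by tumor type and treatment group. It leaves details to the SAP but states neither condition.
- The SAP revision log records only a size rule: "Time to event endpoints to be estimated for trt groups >= 10 patients".
- SAP Section 4, on changes to protocol-specified analyses, mentions neither condition.

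**The concern.** Group size is settled by enrolment. An estimable median is settled by the data. A Kaplan-Meier curve and its landmark estimates can be computed whether or not the curve falls to 50%, so the added words are not needed to make the OS or PFS output computable. They act as a filter on the outcome. For OS and PFS the groups removed are those with the most favorable curves, and the curves that remain understate survival on average.

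The 2-year OS rate is a smaller, connected point. It is a named secondary endpoint (SAP Table 1-1), defined as a proportion, and the SAP does not say that the 24-month Kaplan-Meier estimate is that quantity. A crude proportion would need a rule for patients censored alive before 24 months, and none is given. If the median filter were applied, the Kaplan-Meier estimate would be missing in exactly the groups with an unreached median.

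**Working it through.** The plan gives no survival, response-duration or censoring rates, so there is no planned figure to reproduce. All such rates below are assumptions.

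**1. Chance that the OS median is not reached, complete follow-up.** Let S be the true fraction alive at the end of follow-up, and count the median as reached when the curve touches 50%. The chance of missing it is P(Bin(n, 1 − S) < n/2). Group sizes of 10 to 30 come from SAP 1.1.1. Survival follow-up runs to at least 24 months (Protocol 7.1.7, SAP 2.1.1.5), so two lengths are shown. For 36 months, exponential survival gives S36 = S24^1.5: 0.40^1.5 = 0.253 and 0.50^1.5 = 0.354.

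| n | 24 months, 2-year OS 40% | 24 months, 50% | 36 months, 40% | 36 months, 50% |
|---|---|---|---|---|
| 10 | 16.6% | 37.7% | 2.1% | 9.9% |
| 20 | 12.8% | 41.2% | 0.4% | 5.7% |
| 30 | 9.7% | 42.8% | 0.1% | 3.3% |

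At 2-year OS of 20% or 30% with follow-up ending at 24 months, the figures are 0.6% and 4.7% (n=10) and 0.1% and 1.7% (n=20). The same 24-month formula applies to PFS, with S read as the fraction event-free at the end of follow-up.

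**2. Effect on what is shown.** A simulation with n=30, exponential survival, and exponential censoring at a rate of 20% by 24 months (3,000 runs per case) gave:

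- Follow-up to 24 months: the median was estimable in about 49% of groups at true 2-year OS of 50%, and in 15% at 60%. The mean 24-month estimate among groups passing the filter was 0.42 and 0.45. Over all groups it was 0.50 and 0.60.
- Follow-up to 36 months: the median was estimable in about 94% and 64%, with means among groups passing the filter of 0.49 and 0.56.

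**3. DoR.** The size rule counts patients, not responders. In Protocol Table 14-18, scenario 1 (described there as the data then available), seven groups have at least 10 patients:

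- two have no responder: pancreatic 0/14, CRC RAS wildtype 0/11;
- three have one: DLBCL 1/10, urothelial 1/14, CRC RAS mutant 1/19;
- TNBC has 3/30 and RCC naive at 160 mg has 4/11.

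These may overstate confirmed responses, because interim counts include unconfirmed ones (SAP 2.5.3). With r responders and a fraction q still in response at the end of follow-up, the chance of no median is P(Bin(r, 1 − q) < r/2). For q of 30%, 40% and 50% this is 22%, 35% and 50% with r=3, and 8%, 18% and 31% with r=4.

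**4. Two-year OS as a crude proportion.** Take 30 patients: 9 deaths before 24 months, 6 censored alive before 24 months, and 15 followed alive to 24 months.

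- Censored counted as not reaching 2 years: 15/30 = 50%.
- Censored excluded: 15/24 = 62.5%.
- Censored counted as alive: (15 + 6)/30 = 70%.

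The Kaplan-Meier estimate would lie between 15/24 = 62.5% (all six leave before the first death) and 21/30 = 70% (all leave after the last death).

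**The case against.** **Drafting intent.** The revision log describes only a size rule. Later in the same section, for patients with unknown RAS status, estimable is explained as having enough patients. The sentence listing the landmark times carries no median condition of its own. All this points to loose drafting, and I accept that as the likely explanation. It does not remove the problem: the first sentence covers estimates as well as plots, and a programmer following it would suppress both.

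**DoR.** Here the condition does some work. A group of 10 or more patients may have no responder or one, and a curve is then empty or uninformative. That stands, and it calls for a rule on the number of responders rather than on the median.

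**Delegation.** Protocol 10.5.1 leaves details to the SAP, so the omission from SAP Section 4 is minor. The size rule also departs from the commitment to all contributing groups. Both points stand. In addition, one bullet of the Part 1 conventions in SAP 2.1 is redacted and the output shells are a separate document, so either may narrow the effect.

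**Two-year OS rate.** A reader might infer that the planned rate is biased low. The documents do not support that. SAP 2.6.1 defines the rate but schedules no separate crude analysis, and it does plan a 24-month Kaplan-Meier estimate. Default conventions ("Percentages will be calculated using the number of patients in the relevant population or subgroup as the denominator"; "Unless otherwise specified, the FAS will be the default analysis set used for all analyses") point to the full analysis set as denominator but do not say how early-censored patients enter the numerator, and two of the three counts above give a higher figure.

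A reader might also infer that early censoring is unbounded. Protocol 4.3 ends the study once at least 80% of patients have 24 months of survival follow-up, so on that route about 20% at most fall short. The bound is study-wide rather than per group. It can also be bypassed by early termination (Protocol 4.4) or by transfer: Protocol 4.3 says "The follow-up for disease progression and survival will not be performed or pursued", and SAP 2.1.1.5 says that transferred patients "will not have follow-up for safety, disease progression and survival assessments performed".

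**Conclusion.** The point holds for OS and PFS: as written, the SAP lets the result decide whether Kaplan-Meier output appears, against its own commitment to all contributing groups. For DoR some screen is justified, but the wrong one is used. For the 2-year OS rate the defect is a missing link between the definition and the planned estimator.

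Severity is low. These are descriptive secondary endpoints. Futility and positive conclusions rest on ORR, and ORR, DCR and the listings do not change. The OS effect depends on assumed survival and on follow-up length: with 2-year OS of 40% to 50% it is roughly 10% to 43% of groups if follow-up stops at 24 months, and 0.1% to 9.9% with complete follow-up to 36 months under exponential survival. At 2-year OS of 30% or less, suppression of OS output is uncommon.

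A reader might infer that the condition was added to hide results, or that the trial's conclusions are affected. Nothing in the documents supports either.

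**What to change.** In SAP 2.6.1:

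- Delete the estimable-median condition. For OS and PFS, present curves and landmark estimates for every treatment group of at least 10 patients, and print NE where the median is not reached.
- For DoR, replace the condition with a pre-stated minimum number of confirmed responders, and list individual durations below it.
- State that the 2-year OS rate is the Kaplan-Meier estimate at 24 months with its 90% confidence interval.
- Reconcile the commitment to all contributing groups with whatever limit remains, and record that limit, including the size rule, in SAP Section 4.

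The cost is the wording of two sentences, one clause for DoR and a line in Section 4. No new data are needed.

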2.6.2 Safety objectives

All safety analyses will be based on the safety set (see [Section 2.2.2](#)), which will be used for presenting summaries and listings by treatment groups and overall patients following the general analysis conventions defined under [Section 2.1](#).

The assessment of safety is based on the type and frequency of AEs as well as on the number of laboratory values that fall outside of pre-determined ranges (CTCAE grading limits or normal ranges as appropriate). Other safety data include electrocardiogram and vital signs.

All safety reporting will be based on observation periods defined in [Section 2.1.1.5](#).

Safety summaries (tables, figures) will primarily be based on all data from the on-treatment period with the exception of baseline data which will also be summarized where appropriate (e.g. change from baseline summaries). In addition, a separate summary for death including on treatment and post treatment deaths will be provided. Following the last administration of study treatment, adverse events (including serious adverse events), and new antineoplastic therapies will be collected for a period of 150 days. Following start of new antineoplastic therapy only treatment related adverse events will be collected. Select summaries of related adverse events will be produced for the combined on-treatment and post-treatment periods (see Protocol Section 10.5.2.2).

2.6.2.1 Adverse events (AEs)

Summary tables for adverse events (AEs) will include AEs that started or worsened during the on-treatment period, also termed as treatment-emergent AEs.

AEs will be summarized by number and percentage of patients having at least one AE, having at least one AE in each primary SOC and for each PT. AEs will be coded using the MedDRA and assessed according to the CTCAE version 4.03, respectively. The latest available MedDRA version at the time of the analyses should be used. The MedDRA and CTCAE version used should be specified in the footnote of relevant tables.

A patient with multiple occurrences of an AE will be counted only once in the respective AE category. A patient with multiple CTCAE grades for the same PT will be summarized under the maximum CTCAE grade recorded for the event. AE with missing CTCAE grade will be included in the 'All grades' column of the summary tables. In AE summaries, the primary SOC will be presented alphabetically, and the PTs will be sorted within primary SOC in descending frequency. The sort order of the PTs will be based on their frequency in the most relevant group.

Note: In AE summaries with consolidated study parts, AEs will be presented by study parts, with each part having its own sort order (see General analysis conventions under [Section 2.1](#) for detail).

The following AE summaries will be produced:

- Overview of adverse events (number and % of patients with any AE, any SAE, any fatal SAEs, any AE with dose reductions/interruptions/discontinuations, and correspondingly, with treatment-related AEs; also, AEs requiring additional therapy);
- AEs regardless of study drug relationship by SOC and/or PT, and severity;
- AEs suspected to be study drug related by SOC and/or PT, and severity;
- AEs leading to dose interruption/adjustment regardless of study drug relationship, by SOC and/or PT, and severity;

- AEs leading to dose interruption/adjustment suspected to be study drug related, by SOC and/or PT, and severity;
- AEs leading to study drug discontinuation regardless of study drug relationship by SOC and/or PT, and severity;
- AEs leading to study drug discontinuation suspected to be study drug related by SOC and/or PT, and severity;
- SAEs regardless of study drug relationship by SOC and/or PT, and severity;
- SAEs suspected to be study drug related by SOC and/or PT, and severity;

All AEs collected on the AE eCRF page will be listed with the information collected on those AEs e.g. AE relationship to study drug, AE outcome, etc. AEs with start date in the post-treatment period will be flagged in the listings; those that start in the pre-treatment period will be identified by study day prefixed with a ‘-‘ (a negative sign). Additionally, listings for AEs and SAEs on screened patients who are not treated will be provided with information on those AEs including start-end dates, outcome etc.

